# 1.3 Compliance Statement

This study will be conducted in full accordance all applicable Children's Hospital of Philadelphia Research Policies and Procedures and all applicable Federal and state laws and regulations including 45 CFR 46.

The investigators will perform the study in accordance with this protocol, will obtain consent and assent, and will report unanticipated problems involving risks to subjects or others in accordance with The Children's Hospital of Philadelphia IRB Policies and Procedures and all federal requirements. Collection, recording, and reporting of data will be accurate and will ensure the privacy, health, and welfare of research subjects during and after the study.

### 2 STUDY OBJECTIVES

### 2.1 Primary Aim

The primary aim of this study is to compare effectiveness of the primary care and school interventions to improve asthma control using main and simple effects from the factorial design.

- Specific Aim 1a. Compare the main effects of primary care CHW and school CHW intervention to control group.
- Specific Aim 1b. Compare the differences between children outcomes who receive both interventions (primary care AND school) to only one intervention (primary care OR school).
- *Specific Aim 1c.* Compare each of the active interventions groups (primary care, school, combination) to control.

# 2.2 Secondary Aims

The secondary aim of this study is to explore moderators and mechanisms of effectiveness of the interventions.

- Specific Aim 2a. Investigate moderators of intervention effectiveness outcomes to identify subgroups of children that may be more likely to benefit from the study interventions.
- Specific Aim 2b. Investigate mechanisms of the effect of the intervention, i.e. linkage
  of communications between school and primary care CHWs and daily participation
  in school-based asthma therapy, on asthma control, reduced symptom days, and
  decreased school absences.

#### 3 INVESTIGATIONAL PLAN

# 3.1 General Schema of Study Design

A factorial design will be used to understand the effectiveness of primary care and school CHWs in the implementation of Evidence Based Interventions (EBI) Yes We CanTM Children's Asthma Program in the primary care setting, and Open Airways For Schools® and school-based asthma therapy in the school setting. West Philadelphia children with uncontrolled asthma will be recruited in the Emergency Department or primary care clinic and randomized to a primary care CHW (P+) or usual care (P-), and identified as being in a participating school that has been randomized to a CHW-led school intervention (S+) or none (S-). This study design demonstrates how each sector will be involved in this comprehensive implementation plan. The primary outcomes is asthma control. Secondary outcomes include symptom free days, school absences, hospital and emergency room utilization and cost savings.

This will be a randomized controlled clinical trial of children diagnosed with asthma, ages 5-13 years old randomized after consenting to primary care CHW (P+) or no primary care CHW (P). In the Primary Care Based CHW arm (P+) the CHW will provide one-on-one asthma education in the office and home, environmental trigger mitigation in the home, assistance in identifying care coordination goals with linkages to resources to address barriers and will facilitate communication between the health care provider and the family. The intervention group (P+) will have a total of four visits to the primary care office where they will receive asthma self-management education in the office, review of medications, asthma control assessment, pulmonary function assessment and care coordination. They will receive three intervention home visits where the CHW will reinforce asthma selfmanagement skills, assess the home environment for asthma triggers, provide supplies for environmental remediation and educate caregiver regarding asthma trigger avoidance techniques. This arm will also be eligible for school based direct observed asthma treatment called school-based asthma therapy (SBAT). At twelve months the intervention group will receive an end of study assessment in the primary care office and in the home. The control group will not receive any of the aforementioned services for one year after enrollment. They will be referred to community asthma classes administered by CAPP. After one year the control group will receive one home visit at which time they will receive an environmental home assessment and environmental remediation supplies.

Children in both arms (P+ and P-) may attend an intervention school. Roughly 30 elementary schools have been identified by the School District of Philadelphia to participate in this project. Several public charter schools including three public charter schools served by school-based health centers managed by Education Plus Health have been identified to participate in this study. One half of the schools (S+) will be randomized to receive **Open Airways for Schools** *Plus* designed by Clark, et. al., an EBI asthma education and care coordination model for schools, and School Based Asthma Therapy (directly observed controller medication use).  The remaining half of the identified schools (S-) will be offered training on how to implement the two evidence-based programs in years 4 and 5 of the project.

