### Sites Include:

- CHOP Care Network sites: Cobbs Creek, Karabots and South Philadelphia
- CHOP Emergency Department
- Federally Qualified Health Centers (FQHCs) serving West Philadelphia residents
- The Pediatric and Adolescent Medicine Centers of Philadelphia (PAMCOP) serving West Philadelphia residents

	
 
School District of Philadelphia Public Elementary Schools located in West Philadelphia (including Southwest Philadelphia) who agree to participate
 
Public Charter Schools located in West Philadelphia (including Southwest Philadelphia) who agree to participate
 
					
Study Duration	Active subject participation will last up to 24 months; Medical record review will continue for up to two years from the 12-month follow-up visit or until the data collection period for the study has ended, whichever occurs first. This study is expected to be conducted over six years.					
Study Phases	Screening Study Intervention Study Follow-up					
Efficacy Evaluations	Obtain baseline and follow-up measurements of asthma control, symptoms, patient and caregiver asthma knowledge, presence of environmental triggers, school and work day absenteeism, and healthcare utilization					
Safety Evaluations	Adverse event reports will be collected at each visit. These reports will be reviewed at weekly meetings by the PI to determine if they are a result of the study.  A DSMB has been appointed by the funding sponsor to oversee safety of the interventions.					
Statistical And Analytic Plan	Analysis to be conducted by biostatisticians at the University of Pennsylvania and data managers at the Biostatistics and Data Management Core at CHOP					
DATA AND SAFETY MONITORING PLAN	The PI will be responsible for the study's Data and Safety Monitoring Plan with oversight provided by a DSMB appointed by the NIH.					

TABLE 1: SC	HEI	OULE OF ST	TUDY PRO	OCEDURI	ES						
Study Phase		Screening Treatment/Intervention Follow-Up									
*	Baseline Home Visits		Clinic Visits		12 Mo	12 Mo	Post- 12 Mo				
Visit Number	0	1	HV1	HV2	HV3	2	3	4	HV4	5	6
Informed Consent/Assent	X										
Baseline Questionnaire with Asthma Symptom Recall		X									
Photograph of child's bedroom			X		X				X		
Clinical Assessment – Vital Signs and BMI		X				X	X	X		X	
Pulmonary Function Test		X				X	X	X		X	
Metered Dose Inhaler (MDI) Checklist		X		X		X	X	X		X	
Paediatric Asthma Caregiver's Quality of Life Questionnaire		X								X	
Asthma Control Questionnaire		X				X	X	X		X	X

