Families of children who are not randomized to the primary care intervention will be offered Community Asthma Prevention Program (CAPP) asthma classes, conducted at community sites, which are available to the general public. Data will be collected from the control arm at 3, 6, 9 months by phone or in person. At 12 months an office visit will be scheduled, pulmonary function testing (spirometry) performed and end-of-study data collected. After completing the study these patients will receive one home visit from a primary care CHW to complete an asthma trigger assessment and distribute asthma trigger reduction supplies.

Schools who are not randomized to intervention arm will be offered training after the study data collection period has ended and during the last year of grant funding in how to implement the school asthma interventions and will be provided with information on how to sustain these interventions by obtaining reimbursement from health insurance companies for school CHW services.

During the COVID-19 pandemic, the study activities detailed above will be modified as follows to preserve the health and safety of participants, healthcare professionals, study staff and the West Philadelphia community. Data collection for study visits may take place remotely by telephone or video conference using a HIPAA-compliant application licensed by CHOP. In person clinic visits solely for study purposes will take place as permitted by CHOP Research Institute Policy and Guidelines. Study activities designed to take place in a school setting may take place remotely by telephone or video conference using a HIPPA-compliant application licensed by CHOP.

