5.1.2 Measuring outcomes over time - irregular measurement times

Longitudinal model

Although the protocol calls for regular measurement times (Juniper's **Asthma Control Questionnaire** is a validated survey and will be administered by the CHW at baseline, 3 months, 6 months, 9 months and 12 months), in all likelihood these measurements will have the following characteristics. (1) They will not be administered at 3,6, 9 and 12 months. For some the schedule will lag. (2) Some children will miss one or more of these measurements.

Although some RCTs assume that measurements occur at the protocol-defined time, even when they do not, there is no reason for, and we shall deliberately avoid, that ad hoc practice.

We shall model the time of each measurement as the number of months (including factional amounts) from date of randomization. Time we shall model flexibly with splines. [Here we can use cubic splines as needed).

Choices for knots. We shall assume knots at time 3, 6 and 9 months, the intended dates of measurements.

With time measured flexibly, and with a statistical model that includes time by treatment (4 level) interactions, the spline model will allow for estimate of differences (or ratios) of outcomes at any point along the time (x) axis by treatment group.

Covariates -- selection and balancing

In theory randomization at the child level should balance on observed and unobserved factors. With children spread over 36 schools, and with chance differences across school, imbalances in child characteristics are possible at the school level but are not likely at the treatment assignment level (the four cells a, b, c and d). In addition, dropout can undermine the balance achieved in theory and in practice by randomization.

Key child-level covariates appear in Table 5.1.2.

Table 5.1.2 Covariates – baseline descriptions

Child level factors	Units of measurement or categories
AGE	Subgroups: 5-11; 12-13
GENDER	Male Female
Body mass index (weight in kg) (height in cm)	Collected and/or calculated by age-sex standardized percentile and/or z score. Both percentile and z will be used
HOUSEHOLD CHARACTERISTICS (descriptive only)	 (1) Single Parent/Caregiver vs Multiple Caregivers (2) Number of Adults in household (3) Number of Children in Household
Home environment	Number of bedrooms
Smoking	Smokers or none in home
Caregiver Education Highest level achieved by primary caregiver	Less than HS HS+ Graduate Level
Baseline Healthcare utilization	

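### Protocol 3.1 and 3.1.3 release control schools at conflicting times; the 3.1 rule could expose control children before outcomes are measured, and control families' home visits have a smaller conflict

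*Protocol*

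**What the plan says.** **Control schools.** Protocol 3.1 offers S- schools training by project year: they "will be offered training on how to implement the two evidence-based programs in years 4 and 5 of the project". Protocol 3.1.3 ties the offer to the end of measurement and to funding: they "will be offered training after the study data collection period has ended and during the last year of grant funding". On length, the Synopsis says: "This study is expected to be conducted over six years".

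**Control children.** Protocol 3.1 withholds services for a fixed period from each child's enrolment ("The control group will not receive any of the aforementioned services for one year after enrollment") and then states: "After one year the control group will receive one home visit at which time they will receive an environmental home assessment and environmental remediation supplies". Protocol 3.1.3 describes the 12-month office visit and end-of-study data collection, then says: "After completing the study these patients will receive one home visit from a primary care CHW".

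**Measurement.** The primary endpoint is change in asthma control from Visit 1 to Visit 5 (Protocol 6.3.2). SAP 5.1.2 expects late measurements ("For some the schedule will lag"), models each Asthma Control Questionnaire (ACQ) score at its actual time, and sets no upper limit on that time. SAP 5.4 has rules for a child who changes school. It has none for a control school that takes up the programme during follow-up.

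**The concern.** The S+ v S- contrast requires S- schools to remain at usual practice until their enrolled children have been measured. The 3.1.3 rule secures this; the 3.1 rule does not, because it is tied to a project year and to no outcome. If staff followed 3.1 and an S- school acted on the training while its children were still in follow-up, those children would be analysed as unexposed. The estimated school effect would then move toward zero. No release date is recorded anywhere, so the analyst could not say how many outcomes were affected.

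A milder version applies to P- children. Trigger assessment and remediation supplies are named parts of the P+ package (Protocol 3.1 and 3.1.2). A P- child whose Visit 5 is late could receive them before the final ACQ.

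**Working it through.** **1. School rules side by side.** In a six-year study, year 4 starts at project time 3.0 years and year 5 ends at 5.0 years, so both precede the final year. If funding lasted only five years (the documents do not say), year 5 could coincide with the last grant year, but year 4 still could not. No reading satisfies both rules in full.

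**2. When overlap would occur.** A child enrolled at project time *t* has an on-time Visit 5 at *t* + 1. That falls after the start of year 4 if *t* > 2.0. The documents do not give the enrolment window, so assume uniform enrolment from *s* (0 to 1.0 years) to *r*:

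share measured after year 4 begins = (*r* − 2) / (*r* − *s*)

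| Enrolment ends (*r*) | Share, *s* = 0 | Share, *s* = 1.0 |
|---|---|---|
| 2.0 | 0% | 0% |
| 2.5 | 20% | 33% |
| 3.0 | 33% | 50% |
| 4.0 | 50% | 67% |

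So overlap ranges from none to two thirds, depending on dates that are not given. The SAP shows schools still being randomised in February 2019 (3.1) and counts of evaluable children not yet complete in December 2019 (6.1.1). Without a project start date, neither can be converted to a project year.

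**3. The plan's own power figure.** SAP section 8 states 0.97 for S+ v S- with 432 children, 36 schools, a 0.5 SD effect, no interaction and a design effect of 1.66. By normal approximation with two-sided alpha 0.05:

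- effective n per arm = 432 / 2 / 1.66 = 130.1
- standard error = √(2 / 130.1) = 0.124
- power = Φ(0.5 / 0.124 − 1.96) = 0.98

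This agrees with the simulated 0.97 to about one point, so it can be used for scale.

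**4. Dilution.** Let *q* be the share of S- outcomes measured after release and *f* the fraction of the school effect that a self-run programme delivers. The contrast becomes 0.5 × (1 − *q* × *f*). Both fractions are assumptions.

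| *q* × *f* | Example | Contrast (SD) | Power |
|---|---|---|---|
| 0 | no exposure | 0.50 | 0.98 |
| 0.025 | *q* 10%, *f* 25% | 0.4875 | 0.98 |
| 0.10 | *q* 10%, full delivery | 0.45 | 0.95 |
| 0.20 | *q* 40%, *f* 50% | 0.40 | 0.90 |
| 0.30 | *q* 30%, full delivery | 0.35 | 0.81 |
| 0.50 | *q* 50%, full delivery | 0.25 | 0.52 |

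The full-delivery rows are worst cases.

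The simple contrast S+ without child intervention v neither (b vs d) has less room. Its stated power of 0.83 corresponds to a signal of 1.96 + 0.954 = 2.914 standard errors. Multiplying by 0.975 (0.4875 SD) gives Φ(0.881) = 0.81; multiplying by 0.80 (0.40 SD) gives Φ(0.371) = 0.64.

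**5. Child rules side by side.** Section 3.1 acts one year after enrolment; section 3.1.3 acts after that child completes the study. If Visit 5 is on time, both give the same order. If Visit 5 is late, only 3.1.3 guarantees that the ACQ comes first. The documents do not allow the number of late P- visits to be estimated.

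**The case against.** Several points on the other side stand.

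- **Training is not the intervention.** The tested school programme is run by a study school CHW. School-based therapy is coordinated for children who have both an intervention school and a primary care CHW (Protocol 3.1.3 and 4.4.5). A reader might infer that S- schools would be running the tested programmes during follow-up. The text supports only an offer of training.
- **The child rules can both be obeyed.** Section 3.1 sets a minimum of one year and no due date, while 3.1.3 places the home visit after the 12-month data. Exposure arises only if the one-year mark is treated as a trigger. A reader might also take the child release to be by calendar date, as for schools. It is not: it runs from each child's enrolment.
- **The 24-month participation limit adds little.** Protocol 3.3.1 allows it when assigned interventions are unfinished. P- children have no primary care intervention to finish, and those in S- schools have none at all. It does not show that control children's Visit 5 is generally extended.
- **Dilution might leave a trace.** SAP section 10 specifies a term for period (before or after 14 March 2020) by time by intervention. If release fell after that date, attenuation could contribute to this term, though mixed with pandemic effects.

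What remains is the school contradiction, which none of these points resolves, and the lack of any recorded release date or SAP rule for it.

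**Conclusion.** The conflict over control schools is real and lies in the text: one rule follows the project year, the other follows the end of data collection. Only the second protects S+ v S-. Any early exposure would bias that contrast toward no effect.

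The size is not established. It would be tempting to conclude that overlap is likely, or that a given amount of power has been lost. The documents do not support this, because project start, end of enrolment, *q* and *f* are all unknown. On the illustrative range of 0.49 to 0.40 SD, main-effect power stays at about 0.90 or above, while b vs d power falls to between 0.81 and 0.64.

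The conflict over P- children is smaller: one home visit with supplies, and only when Visit 5 is late.

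**What to change.** - **Schools.** Reconcile Protocol 3.1 with 3.1.3 so that an S- school is offered training only after outcome collection has ended for its own enrolled children.
- **Children.** State in both sections that the P- home visit follows the Visit 5 ACQ or, if that visit is missed, the close of the child's Visit 5 window. The documents give no such window, so one must be set. Without it, a missed visit would delay the supplies indefinitely.
- **Records.** Record the training date for each S- school and the home-visit date for each P- child.
- **SAP.** Keep the as-randomised analysis as primary. Report how many control outcomes were measured after release, and examine their influence only in a sensitivity analysis. Dropping those ACQ values from the main contrast is not advised. Release happens only in control groups, so late attenders would be removed from controls but kept in the intervention arms, which could introduce selection bias and depart from intention to treat.

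The cost is a short protocol amendment, two date fields and a few SAP sentences, with no change in sample size. The downside is that some control schools and families wait slightly longer. If releases have already taken place, the dates and the count of affected outcomes can still be reported.

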### 3.1.1 Screening Phase

We will screen electronic health records to recruit 640 children ages 5-13 years old with uncontrolled asthma (evidenced by one or more asthma exacerbations requiring oral steroids within the past year -OR- two ED visits for asthma within the past year -OR- one hospitalization for asthma within the past year) from several primary care centers (CHOP Care Network – Cobbs Creek, CHOP Care Network - Karabots, CHOP Care Network – South Philadelphia, The Pediatric and Adolescent Medicine Centers of Philadelphia (PAMCOP) and Federally Qualified Health Centers) who live in seven West Philadelphia ZIP codes (19104, 19131, 19139, 19142, 19143, 19151, 19153). In addition, CHOP Emergency Department (ED) will screen and refer children for enrollment when they are seen in the ED. Community partners will also refer children at community events. All screening surveys will be faxed to a confidential fax line and caregivers of all referred patients will be asked if they would like to be screened for study eligibility and participation.

Participants that both meet eligibility criteria and are interested in participation, will be consented/assented using a CHOP IRB reviewed consent form prior to participation in the study. The parent/guardian and the child will have 10 minutes or greater to review the consent form and ask any questions about participation.

### 3.1.2 Primary Care Based Intervention

Children who are randomized to the primary care arm will be assigned a primary care community health worker (CHW). We will implement the *Yes We Can*TM Children's Asthma Program  intervention which is a medical-social model based on a chronic care approach, including risk stratification, clinical care management, social care coordination by a community health worker, and primary care asthma champions. This intervention includes asthma education and trigger reduction visits and care coordination. There will be five clinic visits and four home visits over 12 months implemented by the *primary care CHW* who is integrated into the practice.

Study Visit 1 (primary care office): Once consented and randomized, the CHW will collect baseline data (study questionnaires, weight, height, spirometry), administer a caregiver needs assessment and assist caregiver in choosing 2-3 care coordination goals such as keeping appointments, reduce secondhand smoke exposure or using medications correctly. The CHW will conduct in-office asthma teaching (medications/devices/asthma care plan), coordinate specialist visits and assist caregivers in voicing questions/concerns about medications or treatment plans to the primary care provider. They will personally schedule patients for follow-up visits with the primary care provider. Home Visits 1, 2 and 3: The first three home visits will occur within 2, 4 and 6 weeks after enrollment. At the first visit the CHW will conduct an environmental assessment of the living area and bedroom for common asthma triggers. Based on those findings the CHW will educate regarding asthma trigger avoidance and give supplies to reduce those triggers (mattress and pillow covers, roach bait, mice traps, tiles for carpeted floors) at the second visit. The CHW will also review medications available for the child at home and whether forms/prescriptions have been completed for school. They will coordinate with the primary care team as needed. Video conferencing through a HIPAA-compliant application licensed by CHOP, including but not limited to Vidyo telehealth visits in MyCHOP, may be used for home visits that cannot be conducted in person due to health or safety concerns. For telehealth home visits, supplies will be provided to families via U.S. postal mail with caregivers providing confirmation of receipt. Study Visits 2, 3, and 4 (primary care) will occur at 3, 6, and 9 months post-randomization. At these visits, the participants will receive asthma maintenance care by the provider/clinician and pulmonary function testing (spirometry) in addition to the education and care coordination activities by the CHW as described in the first visit. A member of the research team other than the assigned CHW (Home Visitor) will administer study questionnaires at these visits. At Home Visit 4 at 12 months post-randomization the CHW will conduct an environmental assessment to document trigger reduction techniques in the home and review medications. At Study Visit 5 at 12 months post-randomization, the asthma control questionnaire (ACQ), additional study questionnaires, pulmonary function testing (spirometry) and care coordination goals will be completed. Study staff will administer a CHW satisfaction survey via telephone between 13 and 24 months post-randomization once all primary care and school interventions have been completed.
